Please note that Epidiolex is FDA approved for the treatment of seizures in Lennox-Gestaut syndrome and Dravet syndrome and is clinically used for the treatment of seizures in Sturge-Weber syndrome and many other medically refractory seizure disorders[1-3]. Epidiolex is **no longer** scheduled and can be prescribed clinically for patients seen remotely. We are studying Epidiolex here in Sturge-Weber syndrome for different indications.

Hypothesis: Cannabidiol (Epidiolex) improves SWS brain function resulting in improved cognitive function, social interactions, mood, motor function and behavior, as well as reduced migraines.

2. Objectives (include all primary and secondary objectives)

We propose a follow up to the initial SWS Epidiolex study which suggested improvements in SWS cognitive, social, and behavioral function and in other neurologic issues. **Primary outcome measure:** Quantify cognition 6 months after initiation of Epidiolex compared to baseline. **Secondary outcome**

measures: The following at 6 months compared to baseline: Social function and mood, frequency and severity of seizures, migraine frequency and severity, and motor outcomes.

3. Background (briefly describe pre-clinical and clinical data, current experience with procedures, drug or device, and any other relevant information to justify the research)

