Week 4: Subject will be evaluated at stable dose of Epidiolex. If a subject has side effects thought to be due to study drug on 20 mg/kg/day, or a lower dose, then the dose will be decreased to the maximal dose tolerated in this dose range (5-20 mg/kg/day)

Seizure Medications: The dose of concomitant seizure, mood or behavioral drugs will remain unchanged during CBD treatment unless there are symptoms of toxicity, significant changes in blood levels, or an increase in seizures requiring an increase in a seizure medication. If seizure or mood issues require the addition of a seizure medication, the subject will be taken out of the study.

Recruitment of Participants

Recruitment will be from [name] patients at the Hunter Nelson Sturge-Weber Center database at the Kennedy Krieger Institute. Patients who are in research databases (NA_00043846, NA_00038014) and have given the study team at the Kennedy Krieger Institute permission to contact them regarding research will be sent information regarding the trial and invited to contact the study team for more information if interested. Patients coming for clinical visits to [name] will be pre-screened for meeting inclusion criteria. A log will be kept of patients pre-screened for this trial and results of the pre-screening process.

Information about the pilot study will also be posted on the center websites, clinicaltrials.gov, and offered for posting on the websites of relevant advocacy foundations. If interested, individuals will contact [name] from the website postings. Subjects may also be referred to [name] for research purposes by treating clinicians not on the study team. The investigational nature and objectives of this trial, the procedures, the treatments involved, the attendant risks, and discomforts, as well as potential alternative therapies, will be carefully explained to the patient or their parents or guardian if he/she is a child. A signed informed consent document will be obtained after the entirety of the pilot study is explained. Consent will be obtained by the PI on the trial. Where deemed appropriate by the clinician and the child's parents or guardian, the child will also be included in all discussions about the trial. Assent will be obtained from all children able to provide assent according to our local IRB guidelines. Our consent contains an assent statement on the second-to-last page. The goal is to recruit ten participants total in this study.

Retention Strategies

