Early stopping rules: If a participant experiences a significant health decline or a loss of seizure control (defined as a need to add a new seizure medication), ending assessments will be done, and the subject removed. If the subject experiences a temporary increase in seizures, [name] may take the temporary nature of the increase into account. If the subject has had other benefits to mood, behavior, or neurologic exam that outweigh the risk of an increase in seizures, then [name] may decide to decrease the dose of the study drug since it has been observed that some subjects do well at doses lower than 20 mg/kg/day. Other removal criteria include: death, lost to follow-up, withdrawal of consent for any further data submission, or any other reason the patient, parent, PI or caring physicians think that the subject should be removed. Early withdrawals within the first two months will be replaced.

Study cessation rules. The study will be stopped if any of the following occur: (1) more than 4 subjects drop out because of adverse events probably or definitely **due to study drug** or (2) more than two subjects experience a SAE probably or definitely **due to study drug.** If any subject has a major unexpected negative event (serious injury or death) attributable to the drug, this information will be shared with the other subjects who will have the choice to come off the drug and further enrollment will cease while the event is being fully assessed.

Treatment will continue until any of the following take place:

- 1. Loss of seizure control defined as need to add another seizure medication or other seizure treatment (diet or surgery).
- 2. Intolerable toxicity.
- 3. Pregnancy.
- 4. Withdrawal of consent.
- 5. Six month treatment duration completed as per protocol.
- 6. Laboratory results indicate that the subject's liver function test (ALT or AST) has increased in any of the following ways:
 - >8xULN
 - >5xULN for more than 2 weeks
 - >3xULN and either (TBL >2xULN or INR >1.5)
 - >3xULN with the appearance of fatigue, nausea, vomiting, right upper quadrant pain or tenderness, fever, rash, and/or eosinophilia (>5%)
 - g. Description of what happens to participants receiving therapy when study ends or if a participant's participation in the study ends prematurely.

Extension Phase:

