Those who do not demonstrate a clear benefit after six months of treatment will be weaned off of the study drug over a month, and seen back for one final follow-up visit one month later. All subjects removed early from the study will be requested to complete the end of study assessments while still on study drug; but only if safely possible and with subject consent.

At study's end, any patient doing well on Epidiolex and demonstrating improvement on cognitive, neurologic, mood and/or behavioral assessments may continue on the drug (extension study). Every effort will be made to obtain insurance authorization based on the cognitive and medical improvements

demonstrated by the trial; if required the drug will be provided free of cost to the subject until the drug is approved for clinical use for the treatment of cognitive impairments (or other measured indications) in patients with Sturge-Weber syndrome.

They will then be followed and seen about every 3 months, at which time interim history, including evaluation of side effects and patient reported outcomes, neuroscore, photographs of the port wine birthmark, and the Neuroquality of Life questionnaire will be collected. During the extension phase, the PI will have the ability to change dose (increase and decrease) dose of Epidiolex and other anti-seizure medications as clinically indicated. The maximum dose of Epidiolex will not exceed 20 mg/kg/day. The extension study will consist of at least 4 visits, with the option to remain on the extension study until insurance company approval is obtained for Epidiolex. Study drug will be provided by Greenwich Biosciences until insurance coverage is obtained. The study coordinator will contact the family once per month to ensure the subject is taking the Epidiolex. The study coordinator will ask how much of the Epidiolex the subject has remaining and will ask to see the bottle(s) to confirm.

Lab work (CBC, anticonvulsant levels, and chemistries about every 3 months) will be done as part of clinical care. At all extension study visits, there will be a urine pregnancy test. If the subject is under the age of 18, these results will be given to the parents.

Every six months, an interim analysis will be done of adverse events and outcome measures. Results will be discussed by the Research Investigators and a summary sent to Greenwich Biosciences.

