Study cessation rules. Consideration for stopping the study will occur if any of the following occur. (1) more than 4 subjects drop out of the extension study because of adverse events probably or definitely due to study drug, (2) more than two subjects experience a SAE probably or definitely due to study drug. All subjects will be informed of any SAE due to the study drug.

For those discontinued specifically due to elevated liver function tests, they will continue to be followed until all abnormalities return to the baseline state as assessed by the investigator with AST or ALT <3xULN. Any patient removed early from the study, and all participants at the end of the study wishing to remain [name] patient, will continue to be cared for by [name] and seen at the Hunter Nelson Sturge-Weber Center.

5. Inclusion/Exclusion Criteria

Inclusion criteria: Participants with Sturge-Weber syndrome brain involvement as defined on neuroimaging (n=10 subjects enrolled and on study drug, male and female, ages 3 to 50 years of age) and the following:

- 1. Cognitive impairment defined as a cognitive neuroscore of ≥ 2 at screening.
- 2. Anti-epileptic, mood or behavioral drugs (if on) at stable doses for a minimum of 4 weeks prior to enrollment.
- 3. If present, VNS must be on stable settings for a minimum of 3 months prior to enrollment.
- 4. If on ketogenic or Atkins diet, must be on stable ratio for a minimum of 3 months prior to enrollment.
- 5. Previous subjects who fail at any point to meet continuation criteria and withdraw early may be considered for re-enrollment under a new subject ID as long as the above inclusion criteria are met. The determination of whether to re-enroll will be made by the PI and sponsor on a case-by-case basis. Re-enrollment can occur no earlier than 4 weeks after the final, post-weaning follow-up visit under the old subject ID.

6. Written informed consent obtained from the patient or the patient's legal representative must be obtained prior to beginning treatment.

Exclusion Criteria:

- 1. Patients with any severe and/or uncontrolled medical conditions at randomization such as:
 - a. Liver disease such as cirrhosis, decompensated liver disease, and chronic hepatitis (i.e. quantifiable HBV-DNA and/or positive HbsAg, quantifiable HCV-RNA)
 - b. Uncontrolled diabetes as defined by fasting serum glucose > 1.5
 - c. Active (acute or chronic) or uncontrolled severe infections
 - d. Active, bleeding diathesis

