An earlier study of Epidiolex for medically refractory seizures in Sturge-Weber syndrome suggested improvement in cognition, social, and behavioral outcomes. The side effects experienced were mild and transient.

The proposed trial will be assessing the impact of Epidiolex upon cognitive impairment in Sturge-Weber patients.

c. Justification and safety information if non-FDA approved drugs without an IND will be administered.

Not applicable.

7. Study Statistics

a. Primary outcome variable.

Change in cognitive impairment: Combined score of two NIH Toolbox subtests.

b. Secondary outcome variables.

Change in the following:
SWS neuroscore
Port-wine score
Adverse Events
Seizure severity
Social, behavioral, and mood function
Migraine severity
Motor function

c. Statistical plan including sample size justification and interim data analysis.

Statistical Plan: Results of the above tests will be compared to age normed values. In addition, the difference in results between final test results and initial test results will be obtained for the cognitive functioning score of each subject. Mean and standard deviation of this difference for all 10 subjects on study drug will be calculated. These results will be used to determine whether individuals and the group as a whole demonstrated age normed changes in their cognitive functioning over the course of the six month trial. There is no control group in this study of subjects who are not receiving study drug. The published test-retest standard deviations will be used to determine whether changes in testing results exceed expected test-retest changes in results.

Sample Size Calculation: Since these outcomes will be done for the first time with this drug in SWS, a sample size calculation was not done. Rather, we are estimating that 10 subjects enrolled and on study drug will be sufficient to do the proposed pilot trial and show improvements (or trends for improvement) sufficient to design a future larger clinical trial, or to guide clinical care. This estimate is based on our experience with another trial using the same primary outcome measure.

Interim data analysis: Every week [name] and the study coordinator study will review data for safety. Each month, a formal review of recruitment, safety, data completion and study progress will be made. An

assessment of progress as it relates to study milestones (see **Milestone Table** below) will be made, and a summary report prepared for Greenwich Biosciences.

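### The 6-month seizure comparison has no rule for subjects removed for loss of seizure control, replaced or re-enrolled; limited to completers, it can show a fall with an inert drug

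*Combined protocol and SAP*

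**What the plan says.** - **Outcome.** Section 2 (Objectives) sets as secondary outcomes "The following at 6 months compared to baseline: Social function and mood, frequency and severity of seizures", among others. Section 7b lists seizure severity again. Under Change in Seizure Severity in 4a, baseline frequency is a retrospective count for the month before enrollment, and diaries are used from then on.
- **Removal.** Section 4a (Seizure Medications) says that if seizure or mood problems call for the addition "of a seizure medication, the subject will be taken out of the study". Section 4f (Early stopping rules) repeats this for "a loss of seizure control (defined as a need to add a new seizure medication), ending assessments will be done, and the subject removed".
- **Replacement.** Section 4f: "Early withdrawals within the first two months will be replaced". No exception is made for loss of seizure control.
- **Re-enrollment.** Section 5, inclusion item 5: subjects who withdraw early "may be considered for re-enrollment under a new subject ID", decided case by case.
- **Data at removal.** Section 4g (Extension Phase): subjects removed early "will be requested to complete the end of study assessments while still on study drug; but only if safely possible and with subject consent".
- **Analysis.** Section 7c: "Mean and standard deviation of this difference for all 10 subjects on study drug will be calculated". That sentence concerns the cognitive score. No seizure analysis, analysis set or missing-data rule is given.

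**The concern.** Removal depends on the quantity being compared. A subject whose seizures rise enough to need a new drug leaves before 6 months, and if this happens in the first two months another subject takes the place. A summary of those who reach 6 months then describes subjects who kept seizure control, and the group change moves toward improvement whatever the drug does.

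Adverse event reports, withdrawal records and the per-visit rescue, status epilepticus and emergency counts would still record the worsening, but the reported seizure change need not include it. Section 7c intends the results to help design a larger trial or guide clinical care, so a fall that is partly selection could be carried into either. The limitations paragraph in section 11 concedes small size and no placebo group, but not this selection.

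**Working it through.** The plan states no seizure rate, removal rate or seizure analysis, so it has no figure to reproduce. The check has two parts, and every input marked as assumed is an illustration.

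**1. One replaced removal.** Inputs from the documents: 10 subjects on drug (7c), and 11 consented (4a Study Overview; Milestone Table in 7d). Assumed: the eleventh subject also starts drug, each of 10 completers changes by -20%, and the one removed subject changes by +100%.

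- Completers only: -20%.
- All treated: (10 × (-20) + 1 × 100) / 11 = -100 / 11 = -9%.

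The apparent fall is roughly halved. Its sign does not change.

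**2. An inert drug.** Assumed: one baseline month and six drug months, with 400,000 simulated subjects per setting. Mean seizures are 4, 10 or 30 per month, and monthly variation is Poisson, or Poisson with a monthly gamma factor of shape 5 or 2. A subject is removed in a drug month with at least 2 or 3 times the baseline count and at least 4 more seizures, acted on in 50% or 100% of such months. This makes 36 settings. The change is the group mean in month 6 divided by the group mean at baseline, minus 1. The true change is 0%.

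| Setting | Removed | Completers only | First-two-month removals replaced, later ending values kept |
|---|---|---|---|
| Mean 10, Poisson, 2×, 50% | 15% | -7.7% | -0.5% |
| Mean 10, gamma 5, 3×, 50% | 19% | -13.7% | -0.5% |
| Mean 4, gamma 5, 3×, 50% | 25% | -20.1% | +3.1% |

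- Ten of the 36 settings remove 13% to 26% of subjects. Completers in these show -7.7% to -20.1%. Carrying every removal-month value forward to month 6 gives +5.1% to +19.7% instead, because that month was selected for being high.
- Over all 36 settings the completers' change runs from 0% (mean 30, Poisson, 3×, nobody removed) to -49% (mean 4, gamma 2, 2×, 100%, with 59% removed).
- At a mean of 1 seizure per month (Poisson, 2×, 50%), 2.5% are removed and completers show -4%.

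**Sensitivity to the model.** A second inert-drug model used a mean of about 8 per month, log-normal variation between and within subjects, removal at 2, 3 or 4 times baseline, and the mean log ratio as outcome. Completers show -8% to -60%. Replacing early removals and keeping later ending values gives -2% to -17%. Keeping all ending values gives +4% to +68%. If removal depends on an absolute count instead of a rise from baseline, completers show only -2% to -4%.

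**Chance that it arises.** With an assumed removal risk p per subject, the chance of at least one removal among 10 is 1 - (1 - p)^10: 65% at p = 10% and 89% at p = 20%.

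Re-enrollment was not modelled.

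**The case against.** The best defence is that the plan does not say that the summary is limited to completers. Ending assessments are to be done at removal, and 7c, for cognition, speaks of final and initial results, not of month 6. A natural reading replaces early withdrawals and keeps the ending values of later ones. The table shows that this brings the bias close to zero in the first model. This stands: the direction and size depend on a rule that the plan leaves open.

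The removal proxy is also looser than the protocol. Before a new drug is added, an existing one may be increased (4a), a temporary rise may be tolerated, or the study drug may be reduced (4f). Section 5 requires no minimum seizure rate, and in the earlier study of five patients one had a temporary seizure increase (section 8a). Removals may be few, and with none there is no bias.

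A reader might go further in three ways that the documents do not support:

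- **That several replaced removals could reverse the result.** Two or more would need at least 12 treated subjects, against the 11 planned. The cessation limit in 4f, "more than 4 subjects drop out because of adverse events probably or definitely" due to study drug, does not bound removals for loss of seizure control.
- **That the plan ignores removed subjects.** It asks for their data. The gap is in how the data are used.
- **That re-enrollment inflates the result.** It is discretionary, the inclusion criteria must be met again, and its effect has not been quantified.

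One could also say that counting removals as worse repeats the fault of carrying the removal month forward. It does so only mildly. With a 50% threshold, the true 6-month worse rates in the three examples are 21%, 32% and 37%. Counting removals as worse gives 25%, 36% and 43%, while completers alone give 12%, 22% and 24%.

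**Conclusion.** The point holds as a conditional one. The plan removes subjects on the outcome that it compares, allows their places to be filled, and does not say who is in the seizure summary. If that summary is limited to subjects who reach 6 months, an inert drug can show a fall of about 8% to 20% where 13% to 26% are removed. It can be near zero if removals are rare or later ending values are kept, and an apparent worsening if all removal-month values are carried forward. These sizes rest on assumed seizure rates, variability and removal triggers.

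The documents support saying that the comparison can mislead, not that it will. Severity is minor: this is one of several secondary outcomes in an uncontrolled pilot of 10, and seizures are not the indication under study.

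**What to change.** In 7b/7c, state that:

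- the seizure summary covers every subject who started drug, including replaced subjects and the first course of anyone re-enrolled;
- the number removed for loss of seizure control is reported, and these subjects count as worse in a table of improved, unchanged and worse, with a pre-set threshold (for example a 50% change) and a rule for a seizure-free baseline;
- removals for other reasons are shown separately;
- the completers' change is presented beside this and labelled as completers only;
- the removal-month count is not used as the 6-month value.

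The cost is a few lines of text and one table from data already collected, with no added visits or subjects. The result may look less favourable, and the worse count is slightly conservative, by about 4 to 6 percentage points in the three simulated examples.
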